3.2 Exclusion criteria

1. The patient has persistent clinically significant non-hematologic toxicities \geq Grade 2 (excluding alopecia, nausea, and fatigue).
2. Evidence of CNS involvement.
3. Uncontrolled and active pulmonary disease.
4. Requirement for oxygen treatment.
5. Receiving chemotherapy, radiotherapy or other anti-cancer therapy within 14 days of first dose of study drug. There must be at least a 6-week interval from the last immunotherapy therapy.
6. Uncontrolled infection.
7. HIV/Hepatitis B and/or C.
8. Any history of invasive malignancy in the last 2 years excluding any malignancy such as cervical cancer or skin cancer (excluding melanoma) that is considered cured at the time of screening.
9. Pregnant or breast-feeding woman.
10. Patient has uncontrolled intercurrent illness or medical/psychiatric condition that would limit compliance with study requirements or that would in the Investigator's opinion place the patient at an unacceptably high risk for toxicities.
11. Clinical significant cardiopulmonary disease including uncontrolled or NYHA class 3 or 4 congestive heart failure, uncontrolled angina, uncontrolled hypertension, uncontrolled arrhythmia, myocardial infarction or stroke within 6 months of first protocol treatment or QTc > 480 ms.

4.0 Treatment Plan

4.1 Treatment initiation

Between Day + 45 and Day +180 post HCT if the patient meets the eligibility criteria.

4.2 Treatment duration

- Patients in CRi or PR post-transplant will be treated until disease progression or unacceptable toxicity.
- Patients in CR or CRc post-transplant will be treated for 24 cycles, then:
 - o Patients who are MRD-positive or have different characteristics that, in the opinion of the investigator, put them at a high-risk of relapse, may continue to receive treatment as long as they continue to derive benefit and remain in remission.
 - o Patients who are MRD-negative and don't have other characteristics indicative of high-risk of relapse will stop treatment after 24 cycles, unless the Investigator has a reason to continue treatment (for example, conversion from MRD-positive to MRD-negative only shortly before the 24th cycle).

4.3 Pre-medication

Approximately 60 minutes prior to receiving tagraxofusp.

- Acetaminophen 650 mg PO
- Diphenhydramine 50 mg IV
- Methylprednisolone 50 mg IV (or equivalent dosage of another corticosteroid)
- Ranitidine 50 mg IV (or equivalent dosage of another H2-histamine antagonist)
- Ondansetron 16 mg IV

4.4 Dose and schedule

First three patients:

- Cycles 1-4: Tagraxofusp 9 mcg/kg IV on Days 1, 2, and 3.
- Cycles 5 and beyond: Tagraxofusp 12 mcg/kg IV on Days 1 and 2 (if no unacceptable toxicities at the 9 ug/kg/day IV dose, as defined in the statistical section).

Patient number 4 and beyond:

- Cycles 1-4: Tagraxofusp 12 ug/kg/day IV on Days 1, 2, and 3.
- Cycles 5 and beyond: Tagraxofusp 12 ug/kg/day IV on Days 1 and 2.

Cycle Length: 28 days

During a 28-day cycle, if the patient experiences related non-hematological toxicity with resolution to Grade ≤ 1 or baseline by day 28, the tagraxofusp dose may be continued during the next cycle at the same dose.

Otherwise tagraxofusp-related non-hematological toxicity not resolved to Grade ≤ 1 or baseline by day 28, the start of the next cycle will be delayed until resolution to Grade ≤ 1 or baseline up to a maximum of additional 28 (56 total) days.

After this treatment delay dosing may be continued during the next cycle at same dose.

4.5 Route and Administration

Tagraxofusp is administered by IV infusion via syringe pump over 15 minutes. Prior to infusion, venous access should be established and maintained with sterile 0.9% Sodium Chloride Injection, USP. The total infusion time will be controlled using a syringe pump to deliver the entire dose over 15 minutes.

Attach the tagraxofusp syringe containing the patient's dose to one port and the saline flush syringe to the other port of a Smith's Medical Y connector or equivalent. Clamp off the ports until needed. Attach the opposite end of the Y connector to the microbore tubing. Attach an in-line filter to the opposite end of the microbore tubing. Prime the saline port of the Y connector up to the intersection and clamp shut until the saline flush is required. Next, prime the entire administration set up with the diluted tagraxofusp dose so that it is ready to attach inline. When the tagraxofusp syringe is empty, remove it from the pump and place the saline flush syringe in the syringe pump. Open the clamp on the saline flush side of the Y connector and resume infusion via the syringe pump at the pre-specified flow. Note that the flush syringe will not be emptied entirely at the end of the 15-minute infusion, since it is just intended to push remaining tagraxofusp out of the infusion line to complete drug delivery.

The dose of tagraxofusp will be dependent upon the patient's body weight in kg. The dose for subsequent cycles is to be recalculated only if there is a 10% change in body weight from baseline. The aliquot is calculated from the mg/kg dose x patient weight in kg (all patient doses are calculated in mg/kg body weight). Dose changes should only occur once a cycle has been completed. Intra-cycle dose modifications are not permitted.

Inpatient admission for cycle 1 only (day 1 or one day before day 1). After cycle 1, Tagraxofusp can be administered in the inpatient setting or in a suitable outpatient ambulatory care setting that is equipped for intensive monitoring of patients with hematopoietic malignancies undergoing treatment, per the discretion of the investigator and institutional guidelines and capabilities.

Observation post-dosing should continue until it is clear that the patient does not have evidence/symptoms of capillary leak syndrome (e.g., no weight gain, edema, hypotension, or decrease in albumin) or hypersensitivity reaction. Participants will be monitored as described in Section 5.0, Evaluations During Study.

Supportive care is permitted according to standard institutional/department of MD Anderson Stem Cell Transplantation and Cellular Therapy protocols.

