3.0 Patient Eligibility

3.1 Inclusion criteria

1. Eligible patients will be aged \geq 18 years. Pediatric patients age 2 years and older will be considered on a case by case basis.
2. Diagnosis of Blastic Plasmacytoid Dendritic Cell Neoplasm (BPDCN) according to WHO classification or confirmed by hematopathology.^{24,25}
3. The patients must be in partial response or better (see Appendix A.).
4. $>$ 30 days post-transplant without active or chronic infections.
5. Karnofsky performance status \geq 60%; Lansky \geq 60 (see Appendices B. and C.).

6. LVEF \geq institutional lower limit of normal by MUGA scan or echocardiogram within 30 days of first protocol treatment.
7. Pulmonary function: DLCO, FEV1, FVC $> 40\%$ of predicted value (corrected for hemoglobin) within 3 months of registration.
8. Adequate organ function:
 - a. Serum creatinine ≤ 1.5 mg/dL (133 mmol/L).
 - b. Serum albumin ≥ 3.2 g/dL (or ≥ 32 g/L) without IV albumin within the previous 72 hours.
 - c. Bilirubin $\leq 1.5 \times$ the upper limit of normal ([ULN] except patients with Gilbert syndrome in whom bilirubin level of $> 1.5 \times$ ULN will be allowed).
 - d. AST and ALT ≤ 2.5 times ULN.
 - e. Hemoglobin ≥ 8 g/dL with or without transfusion in the last 7 days.
 - f. Absolute neutrophil count (ANC) ≥ 1000 without GCSF or GM-CSF in the last 2 weeks prior to screening.
 - g. Platelets $\geq 50,000$ /mL.
9. For allo-HCT, no \geq grade 2 visceral (gut or liver) acute GVHD and no \geq grade 3 or any other acute GVHD (Patients with chronic GVHD will be allowed at the discretion of the investigator).
10. Patient agrees to use acceptable contraceptive methods for the duration of time in the study, and to continue to use acceptable contraceptive methods for 2 months after the last tagraxofusp infusion.
11. Woman of child bearing potential (WOCBP) with a negative serum or urine pregnancy test within 14 days of tagraxofusp treatment.
12. Patient or patient's legal representative, parent(s) or guardian able to sign informed consent.
13. The patient can adhere to the study visit schedule and other protocol requirements, including follow-up for survival assessment.

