4.8 Procedures During Dosing Period

Monitor vital signs and check albumin, transaminases, and creatinine prior to preparing each dose of tagraxofusp. During each cycle, testing and procedures that may result in withholding of a scheduled tagraxofusp infusion, largely based on unresolved manifestations of fluid retention and/or other relevant acute toxicities during daily dosing, are described below. Details are presented in Table 3.

Table 3: Recommended Dose Modifications

Parameter	Severity Criteria	Dose Modification
Serum albumin	Serum albumin < 3.5 g/dL or reduced ≥ 0.5 g/dL from value measured prior to initiation of the current cycle	See CLS Management Guidelines (Appendix D.)
Body weight	Body weight increase ≥ 1.5 kg over pretreatment weight on prior treatment day	See CLS Management Guidelines (Appendix D.)
Aspartate aminotransferase (AST) or alanine aminotransferase (ALT)	ALT or AST increase > 5 times the upper limit of normal	Withhold tagraxofusp until transaminase elevations are ≤ 2.5 times the upper limit of normal.
Serum creatinine	Serum creatinine > 1.8 mg/dL (159 micromol/L) or creatinine clearance < 60 mL/minute	Withhold tagraxofusp until serum creatinine resolves to ≤ 1.8 mg/dL (159 micromol/L) or creatinine clearance ≥ 60 mL/minute.
Systolic blood pressure	Systolic blood pressure ≥ 160 mmHg or ≤ 80 mmHg	Withhold tagraxofusp until systolic blood pressure is < 160 mmHg or > 80 mmHg.
Heart rate	Heart rate ≥ 130 bpm or ≤ 40 bpm	Withhold tagraxofusp until heart rate is < 130 bpm or > 40 bpm.
Body temperature	Body temperature $\geq 38^\circ\text{C}$	Withhold tagraxofusp until body temperature is $< 38^\circ\text{C}$.

Parameter	Severity Criteria	Dose Modification
Hypersensitivity reactions	Mild or moderate	Withhold tagraxofusp until resolution of any mild or moderate hypersensitivity reaction. Resume tagraxofusp at the same infusion rate.
	Severe or life-threatening	Discontinue tagraxofusp permanently.

Except in conditions specified above, tagraxofusp may be re-administered subsequently in the same cycle, pending normalization of the abnormalities and pending evidence of stabilization of the underlying clinical conditions resulting in these abnormalities. Postponed doses may be administered within a 10-day period following the initial day of treatment within a cycle.

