8.0 Statistical Considerations

Type of study: Open label, single-arm, single center, Phase 2 clinical trial

Number of patients planned: 20

Expected accrual rate: 5-10 patients/year

Toxicity monitoring

Continuous monitoring of toxicity will be performed in all 20 patients. The first 3 patients will be treated with 9 mcg/kg in first 4 cycles. From cycle 5 and beyond in the first 3 patients, the dose will be 12 ug/kg/day. All subsequent patients will be treated with 12 ug/kg/day. Unacceptable toxicities are defined as tagraxofusp-related toxicities which prevent initiation of Cycle 2 of therapy (Any adverse event ³ grade 3 that is both a) considered related to tagraxofusp, and b) does not resolve to \leq grade 2 after a maximum delay of 56-days). Assuming a prior beta distribution of (0.4, 1.6), corresponding to an unacceptable toxicity rate of 30%, treatment will terminate if the $Pr(dt > 0.20 | \text{data}) > 0.95$, where dt is the toxicity rate attributable to the tagraxofusp treatment. The decision rule for terminating for toxicity is presented in Table 4 and the software used for this Bayesian toxicity monitoring rule is Multc Lean version 2.1.0. The operating characteristics for this rule are presented in Table 5. The method used to produce the decision rule and operating characteristics was designed by Thall, Simon, and Estey ^{26, 27} and extended by Thall and Sung. ²⁸

Table 4 Stopping criteria

Total Patients Enrolled	Stopping Condition (# of patients experiencing unacceptable toxicities)
3-4	3-4
5-8	4-8
9-11	5-11
12-14	6-14
15-18	7-18
19	8-19
20	Patient enrollment ends

Table 5 Operating characteristics

True % of DLTs	Pr (stopping early)	Average # of patients treated
0.05	0.00	20
0.10	0.01	20
0.20	0.11	19
0.30	0.38	16
0.40	0.70	12
0.50	0.91	9

Analysis

Demographic and baseline characteristics will be summarized. Categorical measures will be summarized using frequencies and percentages while continuous variables will be summarized using mean, standard deviation, median, minimum, and maximum.

The primary endpoint of the study is the tolerability of tagraxofusp post-SCT, where tolerability is defined as receipt of at least 75% of planned tagraxofusp doses in at least 4 cycles of therapy. The following table shows the exact 95% confidence intervals for different percentages of patients, out of 20 patients, experiencing tolerability:

Patients experiencing tolerability		95% Exact
Number	Percentage	Confidence Interval
2	10%	1.2% - 31.7%

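### As supplied, the Section 4.5 aliquot instruction works in mg/kg where doses are stated in mcg/kg; in Section 3.1 the platelet minimum is in effect none and the creatinine bracket is off by 1000

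*Combined protocol and SAP*

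**What the plan says.** **Dose.** Section 4.4 sets the dose for the first three patients as "Cycles 1-4: Tagraxofusp 9 mcg/kg IV on Days 1, 2, and 3" and for patient 4 onward as "Cycles 1-4: Tagraxofusp 12 ug/kg/day IV on Days 1, 2, and 3". The toxicity-monitoring text in Section 8.0 agrees: "The first 3 patients will be treated with 9 mcg/kg in first 4 cycles". Section 4.5, the only place that says how the amount for a patient is worked out, uses another unit, twice in one sentence: "The aliquot is calculated from the mg/kg dose x patient weight in kg (all patient doses are calculated in mg/kg body weight". No dose is stated as a number of mg/kg anywhere in the document.

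**Creatinine.** Section 3.1, item 8a, reads "Serum creatinine ≤ 1.5 mg/dL (133 mmol/L". Table 3 in Section 4.8 gives the withholding threshold as "Serum creatinine > 1.8 mg/dL (159 micromol/L".

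**Platelets.** Section 3.1, item 8g, sets the minimum at 50,000 per mL. No second unit stands beside it, and no other section gives a platelet limit.

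**The concern.** Section 4.5 is an operative preparation instruction, not background. As supplied, it points to a figure in mg/kg that the protocol never gives, so whoever prepares the dose must either convert or notice the mismatch. Section 2.3.2 records two Grade 5 cases of capillary leak syndrome with this drug, at 7 and at 16 mcg/kg. With that history, the unit in the calculation sentence should not be left to inference.

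The platelet item decides who may be enrolled. Taken literally, it would exclude almost nobody. Platelets matter here: Section 2.3.2 reports thrombocytopenia in 44 of 125 treated patients (35.2%) and in 23 of 47 with BPDCN (48.9%).

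The creatinine bracket is the least serious of the three. It contradicts a conversion that the protocol itself uses elsewhere, but the limit it annotates is printed next to it in a usable unit.

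**Working it through.** **Inputs**
- Doses: 9 and 12 mcg/kg (Sections 4.4 and 8.0).
- Creatinine limit: 1.5 mg/dL, bracketed as 133 mmol/L (Section 3.1, item 8a).
- Creatinine conversion: 1.8 mg/dL equals 159 micromol/L (Section 4.8, Table 3).
- Platelet limit: 50,000 per mL (Section 3.1, item 8g).
- Body weight: 70 kg, with a range of 50 to 100 kg. This is my assumption; the documents give no weight.

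**1. Creatinine, by the protocol's own factor**
- Factor from Table 3: 159 / 1.8 = 88.33 micromol/L per mg/dL.
- Applied to item 8a: 1.5 × 88.33 = 132.5 micromol/L.
- Table 3's 159 is itself rounded. With 158.5 to 159.5 in its place, the result runs from 1.5 × 158.5 / 1.8 = 132.1 to 1.5 × 159.5 / 1.8 = 132.9 micromol/L.
- So the numeral 133 reproduces in micromol/L, and only the printed unit is off, by a factor of 1000.
- In reverse, 133 mmol/L is 133,000 micromol/L, and 133,000 / 88.33 = about 1,506 mg/dL. That cannot be the equivalent of 1.5 mg/dL.

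**2. Dose, read two ways** (amount = dose per kg × weight)

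| Stated dose | Weight | Converted to mg/kg first | Numeral carried over as mg/kg |
|---|---|---|---|
| 9 mcg/kg | 50 kg | 0.009 × 50 = 0.45 mg | 9 × 50 = 450 mg |
| 9 mcg/kg | 70 kg | 0.009 × 70 = 0.63 mg | 9 × 70 = 630 mg |
| 9 mcg/kg | 100 kg | 0.009 × 100 = 0.90 mg | 9 × 100 = 900 mg |
| 12 mcg/kg | 50 kg | 0.012 × 50 = 0.60 mg | 12 × 50 = 600 mg |
| 12 mcg/kg | 70 kg | 0.012 × 70 = 0.84 mg | 12 × 70 = 840 mg |
| 12 mcg/kg | 100 kg | 0.012 × 100 = 1.20 mg | 12 × 100 = 1,200 mg |

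The first calculation follows Section 4.5 as worded and gives the Section 4.4 dose exactly (0.84 mg is 840 mcg; ratio 1). The second gives 1000 times as much, but only by adding a step that no section calls for.

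**3. Platelets**
- 50,000 per mL / 1000 = 50 per microlitre, which is one thousandth of 50,000 per microlitre.
- There is no internal cross-check. The neutrophil item just above (8f) states no volume unit, and Table 3 has no platelet row.

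**4. Common pattern.** In each case the supplied text has the letter m where a micro sign would remove the difficulty: mg for a microgram unit, mmol/L for micromol/L, mL for microlitre. Other symbols also look damaged. A comparison sign in the Section 8.0 toxicity definition appears as a superscript 3, a Greek letter in Section 2.1.1 appears as a plain a, and a dose in Section 2.3.2 is printed in m/kg/day.

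**The case against.** The strongest objection is that this may not be an error in the plan at all. The text was read from a PDF by a program, the three oddities share one pattern, and similar symbol losses occur elsewhere. Where the unit was typed in ordinary letters (mcg, ug, micromol/L), it is correct. This possibility stands and cannot be excluded from the text supplied. It is not established either. In the Section 8.0 toxicity definition the less-than-or-equal sign survives while its counterpart is damaged, and Section 3.1 keeps its comparison signs while printing mmol/L and mL. That selectivity would also fit symbols already corrupted in the sponsor's own file. Only the source can settle it.

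A reader might infer that Section 4.5 orders a 1000-fold overdose. The documents do not support that. The sentence names a unit and gives no number, and Sections 4.4 and 8.0 are explicit about the unit of the 9 and the 12. The 1000-fold amount needs a further human error.

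A reader might also infer that the creatinine criterion cannot be applied. It can: 1.5 mg/dL is printed and usable, and no patient's eligibility need turn on the bracket.

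On platelets, it is fair to say that nothing else in the protocol contradicts the figure and that a site would probably read it as a slip. That lowers the practical risk. It does not make the criterion correct as written, and no second figure is available to fall back on.

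Two smaller objections stand in full. Mixing mcg and ug is a matter of house style, since they mean the same. And no sample size, stopping rule, endpoint or analysis depends on any of this.

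**Conclusion.** The point holds in a limited form. In the text supplied, the unit in the Section 4.5 calculation conflicts with the unit in which Sections 4.4 and 8.0 state every dose. The size is a factor of 1 if staff convert and 1000 if they carry the numeral over, so this is an invitation to error and not an instruction to overdose. The platelet minimum is 50 per microlitre as printed, in effect no minimum. The creatinine bracket is wrong by 1000 against Table 3, without disabling the limit beside it.

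The milligram amounts rest on the assumed body weights; the ratios do not. The whole conclusion depends on the source file printing mg/kg, mmol/L and per mL. If it does, the dose and platelet items need correction because they are operative text in a trial of a drug with fatal capillary leak syndrome on record. If the source shows micro signs, the plan is not in error on any of the three, and only the optional tidying of mcg and ug remains.

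**What to change.** 1. Check the source file at the three places: the aliquot sentence in Section 4.5, and items 8a and 8g in Section 3.1.
2. If it prints the units shown here, reconcile Section 4.5 with Sections 4.4 and 8.0, using one dose unit spelled out in letters in every section.
3. Have the clinical and pharmacy teams confirm the intended platelet unit in item 8g and correct it. Have them do the same for the creatinine bracket in item 8a, checked against Table 3.

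No dose or eligibility limit is proposed here; the intended values are for those teams to confirm. The cost is a short administrative amendment of a few phrases. Nothing in the statistical section needs to be recalculated.

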4.6 Dose modifications for tagraxofusp related hematological toxicity

It is often very challenging to differentiate disease-related from treatment-related hematological toxicities in patients with BPDCN. Patients with neutropenia, anemia, or thrombocytopenia as a consequence of their disease do not require treatment interruptions for myelosuppression. Dose-interruptions in these patients should be considered on a case-by-case basis and discussed with the PI.

4.7 Discontinuation of treatment

Treatment will continue until maximal duration of maintenance therapy is reached (as specified in Section 4.0, Treatment Duration), or the occurrence of any of the following events:

- Disease progression
- Adverse event(s) that, in the judgment of the Investigator/Medical Monitor, may cause severe or permanent harm or which rule out continuation of maintenance study drug.
- Graft failure
- Development of grade III-IV acute GVHD
- Development of severe chronic GVHD
- Suspected pregnancy
- Inability to start planned cycle of tagraxofusp within 56 days of intended start date of each cycle.
- Major violation of the study protocol (to include subject noncompliance with study medications or protocol-specified procedures) at the discretion of the PI

4.8 Procedures During Dosing Period

Monitor vital signs and check albumin, transaminases, and creatinine prior to preparing each dose of tagraxofusp. During each cycle, testing and procedures that may result in withholding of a scheduled tagraxofusp infusion, largely based on unresolved manifestations of fluid retention and/or other relevant acute toxicities during daily dosing, are described below. Details are presented in Table 3.

Table 3: Recommended Dose Modifications

Parameter	Severity Criteria	Dose Modification
Serum albumin	Serum albumin < 3.5 g/dL or reduced ≥ 0.5 g/dL from value measured prior to initiation of the current cycle	See CLS Management Guidelines (Appendix D.)
Body weight	Body weight increase ≥ 1.5 kg over pretreatment weight on prior treatment day	See CLS Management Guidelines (Appendix D.)
Aspartate aminotransferase (AST) or alanine aminotransferase (ALT)	ALT or AST increase > 5 times the upper limit of normal	Withhold tagraxofusp until transaminase elevations are ≤ 2.5 times the upper limit of normal.
Serum creatinine	Serum creatinine > 1.8 mg/dL (159 micromol/L) or creatinine clearance < 60 mL/minute	Withhold tagraxofusp until serum creatinine resolves to ≤ 1.8 mg/dL (159 micromol/L) or creatinine clearance ≥ 60 mL/minute.
Systolic blood pressure	Systolic blood pressure ≥ 160 mmHg or ≤ 80 mmHg	Withhold tagraxofusp until systolic blood pressure is < 160 mmHg or > 80 mmHg.
Heart rate	Heart rate ≥ 130 bpm or ≤ 40 bpm	Withhold tagraxofusp until heart rate is < 130 bpm or > 40 bpm.
Body temperature	Body temperature $\geq 38^\circ\text{C}$	Withhold tagraxofusp until body temperature is $< 38^\circ\text{C}$.

Parameter	Severity Criteria	Dose Modification
Hypersensitivity reactions	Mild or moderate	Withhold tagraxofusp until resolution of any mild or moderate hypersensitivity reaction. Resume tagraxofusp at the same infusion rate.
	Severe or life-threatening	Discontinue tagraxofusp permanently.

Except in conditions specified above, tagraxofusp may be re-administered subsequently in the same cycle, pending normalization of the abnormalities and pending evidence of stabilization of the underlying clinical conditions resulting in these abnormalities. Postponed doses may be administered within a 10-day period following the initial day of treatment within a cycle.

In the setting of findings possibly consistent with infection, tagraxofusp may be administered pending resolution, provided that an appropriate evaluation for infectious etiologies has been undertaken, and provided that the investigator determines that there is minimal likelihood of uncontrolled systemic infection including sepsis; this may occur on the same day as the temperature elevation, or on subsequent days.

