	Study 0114 (BPDCN)	Study 0114 (AML)	Study 0214	Study 0314	Total
Capillary leak syndrome	9 (19.1)	10 (20.4)		2 (14.3)	4 (26.7)25 (20.0)
Hypokalemia	10 (21.3)	11 (22.4)		1 (7.1)	3 (20.0)25 (20.0)
Febrile neutropenia	5 (10.6)	17 (34.7)		1 (7.1)	023 (18.4)
Insomnia	7 (14.9)	8 (16.3)		2 (14.3)	6 (40.0)23 (18.4)
Cough	3 (6.4)	13 (26.5)		2 (14.3)	4 (26.7)22 (17.6)
Hypocalcemia	11 (23.4)	8 (16.3)		1 (7.1)	2 (13.3)22 (17.6)
Tachycardia	7 (14.9)	10 (20.4)		2 (14.3)	2 (13.3)21 (16.8)
Pain in extremity	5 (10.6)	8 (16.3)		1 (7.1)	5 (33.3)19 (15.2)
Hyponatremia	9 (19.1)	7 (14.3)		1 (7.1)	1 (6.7)18 (14.4)
Neutropenia	8 (17.0)	7 (14.3)		2 (14.3)	1 (6.7)18 (14.4)
Anxiety	9 (19.1)	4 (8.2)		0	4 (26.7)17 (13.6)

Hypertension	10 (21.3)	5 (10.2)	0	2 (13.3)17 (13.6)
Epistaxis	3 (6.4)	11 (22.4)	1 (7.1)	1 (6.7)16 (12.8)
Blood alkaline phosphatase increased	5 (10.6)	9 (18.4)	1 (7.1)	015 (12.0)
Blood lactate dehydrogenase increased	5 (10.6)	8 (16.3)	2 (14.3)	015 (12.0)
Abdominal pain	4 (8.5)	5 (10.2)	2 (14.3)	3 (20.0)14 (11.2)
Blood creatinine increased	6 (12.8)	6 (12.2)	2 (14.3)	014 (11.2)
Hypoxia	3 (6.4)	6 (12.2)	1 (7.1)	3 (20.0)13 (10.4)
Myalgia	1 (2.1)	8 (16.3)	2 (14.3)	2 (13.3)13 (10.4)

In response to the initial case of Grade 5 CLS, which occurred in a patient with BPDCN treated at the 7 mcg/kg dose level early in the clinical program in Study SL-401-0114, all tagraxofusp protocols were amended to exclude patients with left ventricular ejection fraction (LVEF) below the institutional lower limit of normal, and specify that tagraxofusp infusions should be withheld for patients who have an increase in body weight during the dosing period or other potential early evidence of CLS. After the occurrence of Grade 4 CLS, additional precautions were implemented in all tagraxofusp protocols, including instructions that tagraxofusp dosing cease within a given cycle in the setting of substantial albumin reductions or Grade 3 transaminase elevations. The second Grade 5 case of CLS occurred in a patient with AML treated with tagraxofusp at the 16 mcg/kg dose level, in Study STML-401-0114, a dose level above the MTD determined in that study of 12 m/kg/day.

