4.9 Management of Specific Toxicities Capillary leak syndrome (CLS)

Capillary leak syndrome (CLS) is associated with vascular endothelial injury related to tagraxofusp administration and often occurs 3-8 days after initiation of treatment.

See Appendix D. for management of CLS and associated symptoms (hypoalbuminemia, edema, weight gain and hypotension).

In the setting of delays secondary to findings consistent with CLS (i.e., in the setting of resolved hypotension, tachycardia, increased weight, or albumin reductions of a magnitude lower than those warranting withholding of tagraxofusp for the duration of a given cycle), subsequent tagraxofusp is to be administered on days subsequent to the identification of the abnormality (not the same day), pending determination by the investigator that there is no/minimal evidence of ongoing CLS and pending discussion with the PI.

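### Section 2.3.2 and Table 3 do not agree on whether a Grade 3 transaminase elevation ends tagraxofusp dosing for the cycle

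*Combined protocol and SAP*

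**What the plan says.** - **Section 2.3.2 (Safety data).** After Grade 4 CLS occurred, "additional precautions were implemented in all tagraxofusp protocols". They included "instructions that tagraxofusp dosing cease within a given cycle in the setting of substantial albumin reductions or Grade 3 transaminase elevations".
- **Section 4.8, Table 3, AST/ALT row.** The trigger is "ALT or AST increase > 5 times the upper limit of normal". The action is "Withhold tagraxofusp until transaminase elevations are ≤ 2.5 times the upper limit of normal". The row has no higher tier, no stop for the cycle and no pointer to Appendix D.
- **Section 4.8, paragraph after Table 3.** It opens "Except in conditions specified above" and then states that "tagraxofusp may be re-administered subsequently in the same cycle, pending normalization of the abnormalities", adding that the underlying condition must show stabilization. It also sets a time limit: "Postponed doses may be administered within a 10-day period following the initial day of treatment within a cycle".
- **Section 4.9 (CLS).** It speaks of "albumin reductions of a magnitude lower than those warranting withholding of tagraxofusp for the duration of a given cycle", so a whole-cycle hold for albumin is still assumed. It has no counterpart for transaminases. It sends CLS and its associated symptoms to Appendix D and names low albumin, oedema, weight gain and low blood pressure.
- **Section 8.0.** The primary endpoint is tolerability: 75% or more of the planned doses received, with at least four cycles of therapy.

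**The concern.** Section 2.3.2 describes an instruction that ends dosing for the cycle. Table 3 describes a hold that can be lifted within the cycle. Both concern raised transaminases, and nothing in the available text says that this protocol departs from a precaution described as applying to every tagraxofusp protocol.

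Two things are at stake. The first is safety, which is the trial's primary objective: Section 2.3.2 ties the precaution to Grade 4 CLS, and Section 4.9 says CLS often appears 3-8 days after treatment starts, which lies inside the 10-day window for postponed doses. The second is the primary endpoint. It counts doses received, so the rule that sites follow partly determines the result.

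**Working it through.** The plan gives no figure to reproduce on this point. The check is a comparison of passages, followed by a short dose count.

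**1. The two rules side by side**

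| | Section 2.3.2 | Section 4.8 |
|---|---|---|
| Trigger | Grade 3 transaminase elevation | AST or ALT above 5 x ULN, no upper level |
| Action | Dosing ceases within the cycle | Withhold until 2.5 x ULN or below |
| Same-cycle resumption | Not provided for | Allowed, subject to normalization, stabilization and the 10-day window |

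**2. Do the triggers overlap?** Section 6.0 adopts CTCAE version 5.0, but the documents do not print its cut-points. Equating Grade 3 with more than 5 x ULN is therefore an assumption. If Grade 3 begins at 5 x ULN, the two rules cover the same event. If it begins at a higher multiple, the Table 3 row still covers every value above that multiple, because it is unbounded. The conflict remains in both cases.

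**3. Were the other precautions in that part of Section 2.3.2 carried over?** Yes. The LVEF limit is inclusion criterion 6 in Section 3.1, the weight-gain trigger is in Table 3, and the albumin trigger is in Table 3 with a whole-cycle hold implied in Section 4.9. Only the within-cycle stop for transaminases has no counterpart in the available text.

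**4. Effect on dose receipt (illustration)**

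Inputs: Section 4.4 plans three doses in each of Cycles 1-4, so 4 x 3 = 12. Section 4.8 requires transaminases to be checked before each dose is prepared. Assume that the elevation is found before the Day 2 dose and that doses are pooled over Cycles 1-4. Let k be the number of affected cycles.

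- If dosing ceases for the cycle, each affected cycle loses two doses: received = 12 - 2k.
  - k = 1: 10/12 = 83.3%, above 75%.
  - k = 2: 8/12 = 66.7%, below 75%.
- If Table 3 is followed and every postponed dose is given in the window: 12/12 = 100% for either k.
- If Table 3 is followed but recovery misses the window, the remaining doses are lost and the count is again 12 - 2k. The two rules then give the same result.

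So, under these assumptions, a patient's classification changes only with two or more affected cycles and recovery in time. With 20 patients, each reclassified patient moves the tolerability percentage by 1/20 = 5 points.

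**5. How often?** In the BPDCN column of Table 2, ALT increased in 30/47 (63.8%) and AST in 28/47 (59.6%). These are any-grade figures. The Grade 3 share is not given, so the expected number of affected cycles cannot be derived.

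**The case against.** The strongest reply is that Section 2.3.2 is background. It recounts programme history in the past tense and gives sites no instruction, so a site has one operative AST/ALT rule, in Table 3. That stands as to what a site would do. It does not remove the inconsistency, because the text speaks of all tagraxofusp protocols and the companion precautions do appear in this one.

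A reader might infer that no transaminase value, however high, can end dosing for a cycle. The documents do not support that. Resumption needs recovery to the Table 3 level, normalization and stabilization, and a recovery slower than the 10-day window does end dosing for that cycle. Section 4.7 also allows treatment to be stopped for adverse events that the investigator or medical monitor judges potentially severe or permanent in harm.

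The exception clause might be said to supply the missing stop. Its scope is unclear. The AST/ALT row is worded as a hold with a recovery level, which points towards resumption, and the only outright stop visible in Table 3 is for severe or life-threatening hypersensitivity. That is still an interpretation.

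Appendix D might contain a transaminase rule. Its text was not available for this review, and that is not a fault in the plan. Section 4.9 does not list transaminases in its scope and Table 3 sends only albumin and weight there, but neither shows that the appendix is silent.

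On size, the endpoint wording may allow cycles after Cycle 4 to count, so pooling Cycles 1-4 is one reading only. A single affected cycle leaves the patient above 75% on that reading. No effect on the trial's result has been demonstrated.

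**Conclusion.** The passages are inconsistent on whether a Grade 3 transaminase elevation ends dosing for the cycle, and the available text does not resolve it. This should be fixed; confidence is medium, because Appendix D could not be read and the exception clause is open to interpretation.

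It would go too far to conclude that a required CLS safeguard has been dropped, or that sites hold two opposing instructions. The documents show a precaution described in the background that the operative section neither repeats nor explains. They do not show which was intended.

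The possible effect on the endpoint is limited to patients who recover within the window. In the illustration it reaches the 75% threshold only at two affected cycles (8/12 against 12/12). That rests on detection before Day 2, pooling over Cycles 1-4 and delivery of every postponed dose.

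**What to change.** Reconcile Section 2.3.2 with the AST/ALT row of Table 3 and the re-administration sentence below it, so that one rule governs. If this protocol is meant to differ from the precaution in Section 2.3.2, say so there and give the reason. If it is not, make Table 3 and the sentence below it agree with Section 2.3.2. In either case, list the conditions that the exception clause covers, and check that Appendix D is consistent. The choice between the rules is a clinical one for the sponsor; this review does not make it.

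The cost is small: a table row or a background sentence, a clearer exception clause, and a notice to site staff. If the resolution means fewer postponed doses are given, the tolerability percentage may be somewhat lower. Recording whether a dose was omitted or postponed and given because of transaminases would let the effect be seen, but that is optional.
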